The SAFER is a clinician-administered assessment tool designed to structure the evaluation of recent self-harm thoughts and behaviors, including urges, intent, lethality, and contextual risk factors in high-risk clinical populations. The instrument is still under development, and its psychometric properties have not yet been formally established or validated in Brazilian or international samples.

Ascertainment and Adjudication of Suicide Attempts

Suicide attempts will be ascertained at each scheduled assessment using the Columbia–Suicide Severity Rating Scale (C-SSRS), supplemented by weekly safety monitoring calls conducted by a blinded clinical assessor. For each event reported, the attempt date will be established based on participant self-report and, where available, confirmed against clinical or emergency department records. All potential suicide attempt events will be reviewed and adjudicated by a blinded independent clinician —separate from both treatment delivery and primary outcome assessment—using the standardized C-SSRS definitions of an actual suicide attempt. Only the first suicide attempt occurring after randomization will qualify as the primary outcome event for survival analysis; subsequent attempts by the same participant will be recorded as secondary outcomes but will not alter the participant’s censoring status. Participants completing the 6-month follow-up without a confirmed attempt will be censored at day 180. Those who withdraw consent or are lost to follow-up will be censored at the date of last confirmed contact. In cases of irregular follow-up intervals, the last date on which absence of an attempt was confirmed will serve as the censoring date.

Measurement Battery: Prioritization and Burden

The outcome battery was designed to be comprehensive, capturing multiple clinically relevant domains in this high-risk sample. Although several instruments overlap in content—particularly for depressive symptoms (BDI-II, PHQ-9, MADRS) and fatigue (NIH-BFI, FSS)—they serve complementary and non-redundant purposes. The BDI-II is designated the primary self-report measure of depression severity for

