ranked secondary analyses; the PHQ-9 provides a brief screening complement and the MADRS a clinician-rated perspective sensitive to change. Similarly, the NIH-BFI offers a multi-dimensional clinician-rated fatigue assessment, while the FSS captures subjective functional impairment. Instruments measuring religiosity (DUREL), quality of life (SF-12), hypomanic symptoms (HCL-32), sleep (PROMIS), meaning in life (PIL), and subjective well-being (SHS) are included for descriptive and exploratory purposes and are not part of the ranked secondary outcome hierarchy. Assessment burden was considered during protocol development; instruments are administered in a fixed, piloted order, and estimated completion time per assessment visit does not exceed 60 minutes.

Sample size and power

We power the primary analysis (time-to-first attempt) using Schoenfeld's method for Cox models [32]. Assuming a hazard ratio (HR) = 0.50 (BCBT vs ST), two-sided $\alpha=0.05$, and 80% power, the number of required events is:

$$E=[\ln(HR)]^2(Z_{1-\alpha/2}+Z_{1-\beta})^2$$

If the overall 6-month event rate is ~15% in this high-risk sample (e.g., 20% ST vs 10% BCBT), then $N \approx 113$ would be required to accrue ~17 events. To accommodate 25% attrition, we plan $N=150$ (75 per group), yielding $\geq 80\%$ power under these assumptions. This sample also provides $\geq 80\%$ power to detect small-to-moderate between-group effects (e.g., standardized mean difference $d \approx 0.38$) on continuous secondary outcomes with repeated measures.

Statistical analysis plan

- Principles: Intention-to-treat primary; $\alpha=0.05$, two-sided; 95% CIs. Time zero is defined as the date of randomization. Follow-up begins at randomization and continues until first suicide attempt, death, withdrawal of consent, or administrative censoring at the 6-month assessment, whichever occurs first. Any suicide attempt occurring after eligibility screening but before

randomization will be documented as a baseline clinical event but will not count as a primary outcome event; this ensures that the risk period is aligned comparably across both arms from the moment of allocation.

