- Primary analysis: Cox model estimating HR for BCBT vs ST, adjusting for stratification factors (sex, prior suicide attempt), with additional covariates (age and baseline suicidal ideation) included in sensitivity analyses. Check proportional hazards (Schoenfeld residuals); if violated, use time-varying effects or restricted mean survival time. Given approximately 17 anticipated events, including four covariates yields an events-per-variable (EPV) ratio of ~4, below the commonly recommended threshold of 10. To reduce the risk of overfitting, the pre-specified primary model will include only the two stratification factors (sex and prior suicide attempt) as covariates (EPV ~8.5). Adjustment for age and baseline suicidal ideation will be conducted as a supplementary sensitivity analysis.
- Secondary analyses: Linear mixed-effects models (random intercepts) for fixed effects: time, group, group×time; GEE/logistic models for binary outcomes (e.g., any NSSI).
- Missing data: Missing At Random (MAR) is defined as missingness that depends only on observed data; Missing Not At Random (MNAR) refers to missingness that depends on unobserved data (e.g., patients drop out because their suicidal ideation worsened). Time-to-event outcome: participants lost to follow-up will be censored at the date of last confirmed contact. Sensitivity analyses will include: (a) best-case scenario—all BCBT dropouts are assumed attempt-free (censored at day 180) while all ST dropouts are assumed to have attempted at their last contact date; (b)

worst-case scenario—the reverse; (c) tipping-point analysis—identifying the minimum assumed increase in hazard for censored BCBT participants that renders the primary result non-significant.

- Exploratory moderators (hypothesis-generating only): These analyses are explicitly exploratory. Given the projected sample size and anticipated number of primary events, treatment-by-baseline interaction tests are underpowered for definitive subgroup inference and must not be interpreted as confirmatory evidence of effect heterogeneity. Interactions of treatment with baseline factors (e.g., prior attempt, sex, age, baseline symptom severity) will be examined with marginal effects and graphical probes. Mediation (e.g., change in cognitive distortions) may be explored descriptively if data allow. All findings will be framed as generating hypotheses for future adequately powered trials.

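### At the planned 25% attrition the best- and worst-case dropout scenarios are decided largely by their own imputation rule, and the one graded analysis shifts only the BCBT arm and needs a significant primary result

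*Protocol*

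**What the plan says.** In the protocol's Statistical analysis plan, under Missing data, participants lost to follow-up are censored at last confirmed contact in the primary analysis. Three sensitivity analyses follow:

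- (a) Best case: "all BCBT dropouts are assumed attempt-free (censored at day 180) while all ST dropouts are assumed to have attempted at their last contact date".
- (b) Worst case: the two arms swap roles.
- (c) Tipping point: "identifying the minimum assumed increase in hazard for censored BCBT participants that renders the primary result non-significant".

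The same bullet gives, as its example of data missing not at random, patients who leave because their ideation has worsened. That example is not tied to one arm.

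Sample size and power plans 150 participants, 75 per group, with 25% attrition, attempt risks of 20% (ST) and 10% (BCBT), and a sample that "would be required to accrue ~17 events". Ascertainment and Adjudication of Suicide Attempts adds: "Participants completing the 6-month follow-up without a confirmed attempt will be censored at day 180".

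**The concern.** A sensitivity analysis should separate a result that survives plausible departures from the missing-data assumption from one that does not. Scenarios (a) and (b) assign attempts to 100% of dropouts in one arm and to 0% in the other. If there are as many dropouts as real events, the rule outweighs the data, and the two scenarios point in opposite directions almost regardless of what was observed.

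That leaves (c) as the only graded analysis, and its wording is narrow in three ways:

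- It changes the hazard in the BCBT arm only.
- It is defined by the loss of significance, so it has no output when the primary result is not significant.
- Its target group, read literally, includes BCBT completers, who are also censored (at day 180) and whose outcome is known.

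At stake is how far the sole confirmatory result can be interpreted if about a quarter of the sample is lost. In particular, a null finding could be masked by informative dropout from ST, and no listed graded analysis examines that.

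**Working it through.** **Inputs from the protocol.** 75 per arm; 25% attrition; 6-month risks 20% and 10%, about 15% overall; about 17 events; 180 days of follow-up; scenario rules (a) to (c).

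**The plan's own figures.** 17 / 0.15 = 113 and 113 / 0.75 = 151, against 150 stated, so these steps reproduce. The 17 does not: Schoenfeld's formula with 1:1 allocation gives 4 × (1.96 + 0.84)² / (ln 0.50)², which is 66 events. Leaving out the factor 4 gives 16.3. That is a separate matter and affects this point only through power.

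**Counts.** 0.25 × 75 = 18.75, about 19 dropouts per arm, or about 17 to 18 once attempts before dropout are removed. At 20% versus 10%, mean observed attempts are about 13.2 (ST) and 6.5 (BCBT), 19.7 in all.

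- (a): ST 13.2 + 16.9 = 30.1 against BCBT 6.5.
- (b): ST 13.2 against BCBT 6.5 + 17.7 = 24.2.

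**Simulation.** 4,000 trials per setting, exponential attempt times, unadjusted Cox HR with log-rank z. Assumptions not in the protocol: dropout is equal in the arms, uniform over 180 days and unrelated to risk.

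| ST / BCBT risk | Dropout | Primary: median HR | (a): median HR; significant for BCBT | (b): median HR; significant for BCBT; significant against BCBT |
|---|---|---|---|---|
| 15% / 15% | 25% | 0.99 | 0.31; 92% | 3.16; 0%; 92% |
| 20% / 10% | 25% | 0.47 | 0.18; 99.5% | 2.01; 0%; 55% |
| 20% / 10% | 15% | 0.47 | 0.25; 95% | 1.29; 0.3%; 11% |
| 20% / 10% | 10% | 0.47 | 0.30; 85% | 1.00; 2%; 3% |
| 20% / 10% | 5% | 0.46 | 0.36; 67% | 0.72; 13%; 0.4% |

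At 20% / 10% and 25% dropout, (b) had HR > 1 in 98% of trials. Among trials with a significant primary result for BCBT, (b) had HR > 1 in 96% and stayed significant for BCBT in none. With unequal dropout (ST/BCBT 20/30 or 30/20), (b) was significant against BCBT in 74% and 35%.

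**When (c) has a starting point.** At 20% / 10% and 25% dropout the primary test was significant in about 36% of trials, so (c) as worded would be undefined in about 64%. Most of that reflects the event shortfall. Even at the stated 80% power, 20% of trials would have no tipping point to report.

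**Who is shifted in (c).** In the BCBT arm, 75 − 6.5 − 17.7 leaves about 51 completers against about 18 early dropouts. The completers are unaffected if the raised hazard stops at day 180, but the protocol gives no end date for it.

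**What a graded two-arm shift looks like.** The post-dropout hazard was multiplied by a factor in each arm (20% / 10%, 25% dropout, 1,500 trials per cell, true hazards used, so this is illustrative only). Median HR by ST/BCBT multiplier: 1/1 0.48; 1/2 0.52; 1/3 0.58; 1/5 0.69; 2/1 0.43; 3/1 0.40; 5/1 0.34; 3/3 0.47; 5/5 0.48. The range 0.34 to 0.69 compares with 0.18 and 2.01 for (a) and (b).

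**The case against.** The strongest reply is that (c) already does the essential job. In a superiority trial the main threat is a false claim of benefit, and raising the hazard of censored BCBT participants until significance is lost tests that in the conservative direction. This stands. A reader might infer that the effect of withdrawal on the primary outcome is not tested at all; the text does not support that.

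A reader might also infer that (a) and (b) give the same answer whatever the truth. They do not. At 10% dropout (b) has median HR 1.00, and at 5% it is 0.72. At 25% dropout with a much larger effect (40% versus 10%, outside the protocol's rates), its median is 0.87. The 25% is a sample-size allowance, and weekly calls and the exclusion of people without reliable contact may keep loss below it. Even at 25%, significant reversal in (b) is far from certain (55%).

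A third tempting reading is that someone who stops therapy but keeps answering calls would count as a dropout and lose known attempt-free time. The protocol excludes this: the preceding sentence concerns loss to follow-up, the analysis is by intention to treat, stopping therapy is not among the events that end follow-up, and completers are censored at day 180. Nor is it a contradiction that imputed attempts fall at last contact although, for irregular intervals, "the last date on which absence of an attempt was confirmed will serve as the censoring date". Placing failure there is a deliberate extreme, and no numerical consequence has been shown.

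Finally, (a) and (b) are already named as best and worst cases and carry no confirmatory weight, the list is not stated to be exhaustive, and a separate analysis plan could add more. This lowers the priority. It does not remove the point, because the protocol itself fixes these three analyses, and the graded one is worded too narrowly.

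**Conclusion.** The point holds as a cheap improvement. At attrition near the planned 25%, with no effect or the planned effect, (a) and (b) are settled largely by the imputation rule. The best case is significant for BCBT in about 92% of null trials, and the worst case does not confirm the planned benefit in any simulated trial. Neither can be used to judge robustness at that level of loss; at about 10% or less, (b) does become informative. Analysis (c) is valid for a significant BCBT benefit, but it covers one arm, gives nothing for a non-significant result, and names a group that literally includes completers. The percentages rest on equal, uniform, non-informative dropout. The 64% figure for (c) should carry little weight here, since it comes mainly from the separate event-count problem.

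**What to change.** Keep (a) and (b), and state that they are extreme bounds not used to judge robustness. Extend (c) as follows:

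- Use delta-adjusted multiple imputation of event times from the censoring date to day 180, only for participants censored before day 180.
- Multiply the post-censoring hazard by a pre-specified grid, for example 1, 1.5, 2, 3 and 5, separately in each arm.
- Report the HR and 95% CI over the two-way grid whether or not the primary result is significant, and mark the tipping point where one exists.

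The cost is a wording change and a little more analysis work, with no new data or participants. The drawback is that the grid must be chosen in advance, and the choice of its upper end is a matter of judgement.

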Brief Cognitive-Behavioral Therapy for Suicide Prevention in a Brazilian Outpatient Sample (BCBT-BR): Protocol for a Two-Arm Randomized Controlled Trial

Short title: BCBT-BR Trial Protocol

Date: May 4th, 2026

Abstract

Importance: Suicide remains a leading cause of premature mortality worldwide. While global rates have declined since 2000, the Region of the Americas shows concerning increases, particularly in Brazil. Brief Cognitive-Behavioral Therapy (BCBT) has demonstrated efficacy in reducing suicide attempts in high-income countries, but evidence from low- and middle-income countries (LMICs) and civilian outpatient settings remains limited.

Objective: To evaluate whether BCBT reduces suicide attempt incidence over 6 months compared with manualized Supportive Psychotherapy (ST) among high-risk Brazilian adults receiving university outpatient care.

Design, Setting, and Participants: Single-site, parallel-group, superiority randomized clinical trial (RCT) at the Institute of Psychiatry, University of São Paulo, Brazil. Adults aged 18-65 years with current suicidal ideation and/or suicide attempt within the past month will be randomized 1:1 to receive 12 weekly 60-minute sessions of BCBT or dose-matched ST (N=150; 75/group).

Interventions: BCBT targeting emotion regulation and cognitive reappraisal versus manualized ST providing emotional support without systematic skills training.

Main Outcomes and Measures: Primary outcome is time-to-first suicide attempt over 6 months, assessed by blinded evaluators. Secondary outcomes include suicidal ideation, non-suicidal self-injury, depression, anxiety, treatment feasibility and acceptability. Assessments occur at baseline, mid-treatment (week 6), end-of-treatment (week 12), and 3- and 6-month follow-ups, with weekly attempt surveillance. Intention-to-treat analyses will employ Cox proportional hazards regression (primary outcome) and mixed-effects/generalized linear models (secondary outcomes). Sample size provides 80% power to detect HR=0.50 ($\alpha=0.05$, 25% attrition).

Conclusions and Relevance: This trial will provide critical evidence on BCBT effectiveness in LMIC outpatient settings, informing scalable suicide prevention strategies.

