Secondary objectives: Compare trajectories of suicidal ideation, NSSI, depression, and anxiety; evaluate feasibility/acceptability; explore predictors and moderators of response (e.g., prior attempts, sex, age, symptom severity).

Hypotheses

1. BCBT will yield a lower hazard of suicide attempt (superiority).

2. BCBT and ST will show similar improvements in general anxiety/depression, but BCBT will outperform ST on suicide-related outcomes.
3. BCBT will demonstrate high feasibility and acceptability in this population, as reflected by satisfactory recruitment rates, session attendance, treatment adherence, and positive patient satisfaction ratings.
4. Baseline characteristics, including history of prior suicide attempts, baseline symptom severity, age, and sex, will be associated with differential clinical outcomes over follow-up.

Methods

Trial Design

Single-site, parallel-group, superiority RCT (1:1) with blinded outcome assessment and 6-month follow-up. The protocol follows the SPIRIT 2025 guidelines; reporting will follow the CONSORT 2025 guidelines and the extensions for non-pharmacological interventions and harms.

Randomization

Participants will be randomly assigned in a 1:1 ratio, stratified by sex and prior suicide attempt, using a computer-generated permuted-block randomization sequence with variable block sizes (blocks of 4 and 6) to prevent allocation prediction. The sequence will be generated by an independent researcher with no involvement in participant recruitment or outcome assessment, using validated statistical software. Participants will be enrolled by the study coordinator; treatment allocation will be released only after eligibility is formally confirmed and informed consent is obtained. Allocation concealment will be maintained through a centralized, web-based randomization module within REDCap, which withholds the assigned arm until the enrollment step is completed and locked. Neither the enrolling clinician nor the participant will have access to forthcoming allocations.

Blinding

Given the nature of psychotherapy research, blinding of participants and therapists to treatment allocation is not feasible (Cuijpers et al., 2015). However, all outcome

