assessors (blinded evaluators) will be masked to treatment assignment throughout the study. Blinded evaluators are trained research assistants with no involvement in treatment delivery or session documentation. Participants will be instructed at enrollment not to disclose their treatment condition during assessment visits, and assessments will be conducted in a separate physical or virtual space from therapy rooms. Blinded evaluators will not have access to session notes, therapist logs, or any allocation-linked material. Blinding integrity will not be formally assessed; however, procedures to minimize unblinding include instructing participants not to disclose their treatment condition, conducting assessments in settings separate from therapy sessions, and restricting blinded evaluators' access to treatment-related materials.

Study setting

Institute of Psychiatry of the Hospital das Clínicas, Faculty of Medicine, University of São Paulo, is the selected study site for this randomized controlled trial.

Eligibility criteria

a. Inclusion:

1. Age 18–65 years.
2. Treatment-seeking outpatient or recent psychiatric inpatient discharge ≤ 30 days.
3. Current suicidal ideation during the past week and/or suicide attempt within the past month.
4. Ability to consent and communicate in Brazilian Portuguese.

b. Exclusion:

1. Acute psychosis or mania precluding psychotherapy participation.
2. Substance intoxication/withdrawal requiring stabilization.
3. Immediate need for inpatient admission at screening.

4. Severe cognitive impairment/neurocognitive disorder; moderate–severe intellectual disability.
5. Inability to attend visits or lack of reliable contact for safety monitoring.

Training, Supervision, and monitoring of study clinicians

Two clinicians will be assigned to provide both groups' treatments. Training will consist of sessions with didactic instruction, live supervised role plays with feedback, assigned reading materials, and supervision throughout the process. The main reference will be the BCBT manual, elaborated by Rudd & Bryan (2018), which contains clinical practice guidelines. To enhance the treatment credibility, fidelity checklists will be used and checked upon supervision by the researchers.

Concomitant Treatments

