The PROMIS Sleep Disturbance item banks evaluate subjective sleep quality, depth, restoration, and difficulties initiating or maintaining sleep (Buysse et al., 2010). Developed within the NIH PROMIS framework using item response theory, these scales offer high precision across severity levels. While Portuguese translations exist, comprehensive Brazilian validation studies remain scarce.

Montgomery–Åsberg Depression Rating Scale (MADRS)

The MADRS is widely used to assess the severity of depressive symptoms in both clinical and research settings (Montgomery & Åsberg, 1979). Composed of 10 items scored from 0 to 6, the scale evaluates symptoms such as sadness, anxiety, reduced concentration, and appetite changes. Studies have demonstrated its high sensitivity to changes in depression severity over time, and it has been validated in Brazilian samples (Fernandes, Carneiro et al., 2019). Scores will be analyzed as continuous variables and categorized according to established depression severity levels.

Columbia–Suicide Severity Rating Scale (C-SSRS)

The C-SSRS is a widely used instrument for assessing suicidal ideation and behavior (Posner, Oquendo et al., 2007). It categorizes the severity of suicidal ideation into five levels, ranging from “wish to be dead” to “active suicidal ideation with specific plan and intent.” The scale also captures the occurrence of actual, interrupted, or aborted suicide attempts, as well as preparatory behaviors. The C-SSRS identifies the highest level of ideation and suicidal behaviors since the last assessment, providing essential information for clinical decision-making. It has demonstrated strong psychometric properties (Posner, Brown et al., 2011) and, although it has not been formally validated in Brazilian Portuguese, it was previously

translated by the original authors and has been used in studies involving similar populations (Anzolin, Baldez et al., 2024).

NIH Brief Fatigue Inventory (BFI)

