- Multiplicity: The primary outcome (time-to-first suicide attempt) is the sole pre-specified confirmatory endpoint, tested at two-sided $\alpha=0.05$. Secondary outcomes are organized in the following interpretive hierarchy: (1) suicidal ideation (BSI, C-SSRS ideation subscale); (2) non-suicidal self-injury (DSHI-s); (3) depressive symptoms (BDI-II); (4) anxiety (GAD-7); (5) treatment feasibility and acceptability. No formal α -adjustment is planned across secondary outcomes; results should be interpreted in light of the number of comparisons made and regarded as exploratory. Exploratory moderator and mediator analyses carry no inferential weight regarding treatment efficacy and will be clearly labelled as hypothesis-generating throughout the manuscript.

Data capture and management

REDCap with role-based access, audit trails, range checks, and encrypted storage. Identifiers stored separately; audio files on secure institutional servers. Only authorized personnel access identifiable data.

Monitoring and safety

Independent Data and Safety Monitoring Board (DSMB) reviews SAEs quarterly (or ad hoc) and may recommend protocol modifications or early termination for safety. AEs/SAEs reported to CEP/CONEP per Brazilian regulation. Participants receive 24/7 emergency contacts.

Discussion

The BCBT-BR trial rigorously evaluates whether suicide-specific CBT confers advantages over common-factor ST in a Brazilian outpatient setting. Strengths include an active comparator, blinded assessment, event-focused primary outcome, therapist cross-training with fidelity checks, and cultural adaptation. Findings will guide scalable implementation of suicide-focused care in LMIC public mental health systems.

Ethics and Registration

Ethics: CONEP/Plataforma Brasil approval CAAE 88755725.9.0000.0068

Registration: ClinicalTrials.gov [registration pending; CAAE 88755725.9.0000.0068 refers to the Brazilian ethics approval (CONEP/Plataforma Brasil) and is reported separately above] 88755725.9.0000.0068

Protocol amendments: Any substantial changes will be submitted to ethics committees and updated in registries.

Funding

There is no funding for this trial. RFD receives scholarship from São Paulo Research Foundation (FAPESP) (#2024/10058-0).

Author Contributions

- Conceptualization: [name] (LB), [name] (RFD), [name] (ECM), [name] (CB)
- Methodology: LB, [name] (RERF), CB, RFD

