
Supplementary Material

Table 1: The structure and components of BCBT (Bryan & Rudd, 2018)

Phase	1	2	3
Sessions	1-5	6-10	11-12
Therapeutic component	Emotional Regulation and Crisis Management	Targeting Belief Systems Related to Suicide	Relapse Prevention
Techniques	Crisis Response Plan; Means restriction counseling; Sleep stimulus control; Relaxation skills training; Mindfulness skills training; Reasons for living list; Survival kitk.	ABC Worksheet ; Challenging Questions Worksheet; Problematic Patterns of Thinking Worksheet; Activity planning; Coping cards.	Relapse prevention task.

Table 2: Assessment schedule

Schedule of Assessments (CONSORT format)

Measure	T0	T1	T2	T3	T4	T5	T6	T7	T8	T9	T10	T11	T12	T13	T14	T15
Sociodemographic	X															
Treatment History	X															
Weekly Follow-up		X	X	X	X	X	X	X	X	X	X	X	X	X	X	X
BSI	X	X	X	X	X	X	X	X	X	X	X	X	X	X	X	X
BDI-II	X	X	X	X	X	X	X	X	X	X	X	X	X	X	X	X
DUREL	X	X	X	X	X	X	X	X	X	X	X	X	X	X	X	X
GAD-7	X	X	X	X	X	X	X	X	X	X	X	X	X	X	X	X
PHQ-9	X	X	X	X	X	X	X	X	X	X	X	X	X	X	X	X
PIL	X	X	X	X	X	X	X	X	X	X	X	X	X	X	X	X
SHS	X	X	X	X	X	X	X	X	X	X	X	X	X	X	X	X
SF-12	X	X	X	X	X	X	X	X	X	X	X	X	X	X	X	X
HCL-32	X	X	X	X	X	X	X	X	X	X	X	X	X	X	X	X
PROMIS Sleep	X	X	X	X	X	X	X	X	X	X	X	X	X	X	X	X
MADRS		X	X	X	X	X	X	X	X	X	X	X	X	X	X	X
C-SSRS		X	X	X	X	X	X	X	X	X	X	X	X	X	X	X
NIH BFI		X	X	X	X	X	X	X	X	X	X	X	X	X	X	X
FSS		X	X	X	X	X	X	X	X	X	X	X	X	X	X	X
SCS-R	X	X	X	X	X	X	X	X	X	X	X	X	X	X	X	X
SAFER	X	X	X	X	X	X	X	X	X	X	X	X	X	X	X	X
SAFER Follow-Up														X	X	X

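### Table 2 schedules no T0 value for the C-SSRS, MADRS, NIH-BFI and FSS, so a joint first-ranked secondary measure and three unranked scales have no documented pre-allocation baseline

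*Protocol*

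**What the plan says.** - **Schedule.** In the Supplementary Material, Table 2 ("Schedule of Assessments (CONSORT format") has 16 columns, T0 to T15. The C-SSRS, MADRS, NIH BFI and FSS rows are empty at T0 and marked at T1–T15. BSI, BDI-II, GAD-7, PHQ-9, SCS-R and SAFER, among others, are marked at T0 as well. No section gives calendar times for the columns.
- **Baseline promised.** Abstract, Main Outcomes and Measures: "Assessments occur at baseline, mid-treatment (week 6), end-of-treatment (week 12), and 3- and 6-month follow-ups, with weekly attempt surveillance". Under Ascertainment and Adjudication of Suicide Attempts, the C-SSRS is to be used at every scheduled assessment.
- **Rank.** Statistical analysis plan, Multiplicity, lists first "1) suicidal ideation (BSI, C-SSRS ideation subscale". Depression is represented there by the BDI-II. MADRS, NIH-BFI and FSS are not named in the hierarchy.
- **Analysis.** Secondary continuous outcomes go into random-intercept linear mixed models with time, group and group×time.
- **Recall window.** The instrument description states: "The C-SSRS identifies the highest level of ideation and suicidal behaviors since the last assessment".
- **Entry and allocation.** Inclusion item 3 reads "Current suicidal ideation during the past week and/or suicide attempt within the past month". Under Randomization, "treatment allocation will be released only after eligibility is formally confirmed and informed consent is obtained"; completion of a baseline battery is not named as a condition.

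**The concern.** A group×time term measures how the arms diverge from the first recorded visit. If that visit follows allocation, whatever BCBT has achieved by then is absorbed into the starting difference and disappears from the interaction. A value on the same scale from before allocation is also the most useful covariate for precision, and it cannot be recovered once the visit has passed. This is therefore a data-collection matter that a later analysis plan cannot repair.

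An early effect is plausible on the protocol's own account: Table 1 places the crisis response plan in the first phase of BCBT (sessions 1–5).

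There is a smaller point for the primary endpoint. The first C-SSRS asks about the time since the last assessment, and no earlier C-SSRS is scheduled. Some participants enter because of an attempt in the preceding month, so the opening window needs a defined start.

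**Working it through.** **1. Is T0 the baseline, and are the blanks real?**
- Each of the four rows has 16 cells with the first empty, the same column count as the complete rows. A column shift in text extraction is therefore unlikely.
- The sociodemographic and treatment-history forms appear only at T0, and Weekly Follow-up starts at T1. T1–T12 matches the 12 weekly sessions, and SAFER Follow-Up starts at T13. T0 reads as baseline and T1 as the first week.
- A split between self-report at T0 and clinician ratings from T1 does not explain the pattern. SAFER is clinician-administered yet marked at T0, and the FSS is self-report yet blank.
- The blanks conflict with the baseline in the abstract and with use of the C-SSRS at every scheduled assessment.

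**2. The plan's own power figure.** Sample size and power states at least 80% power at d ≈ 0.38 with repeated measures. It gives neither the correlation r nor the number of visits k, so the figure has no unique reproduction. With 75 per arm:
- One time point: SE = √(2/75) = 0.163; power 64%.
- Mean of k = 4 post values, r = 0.5: variance (1 + 3r)/4 = 0.625; SE = √(2 × 0.625/75) = 0.129; power 84% without any baseline.
- The same with a T0 covariate: variance 0.625 − r² = 0.375; SE = 0.100; power 97%.

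The stated figure is thus reachable without a baseline, under assumptions the protocol does not state.

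**3. What the missing T0 costs a group×time contrast.** Inputs from the protocol: d = 0.38, two-sided α = 0.05, 75 per arm and 25% attrition, so 75 × 0.75 ≈ 56 completers per arm. Assumptions: r = 0.6 between any two visits, unit SD, and a share f of the final effect already present at T1.

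- Baseline-adjusted (ANCOVA on T0): SE = √(2(1 − r²)/n) = √(2 × 0.64/56) = 0.151.
- Change from first visit: SE = √(4(1 − r)/n) = √(1.6/56) = 0.169, with expected difference 0.38(1 − f). With complete data and categorical time, this is also the final-versus-first-visit contrast of a random-intercept model.
- Power = Φ(difference/SE − 1.96).

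| Analysis | Expected difference | Power, r = 0.6 | r = 0.5 | r = 0.7 |
|---|---|---|---|---|
| ANCOVA on T0 | 0.38 | 71% | 64% | 80% |
| Change from T1, f = 0 | 0.38 | 61% | 52% | 74% |
| Change from T1, f = 0.08 | 0.35 | 54% | 46% | 67% |
| Change from T1, f = 0.30 | 0.27 | 35% | 29% | 44% |
| Final visit only, no baseline | 0.38 | 52% | 52% | 52% |

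An f of 0.08 corresponds to linear build-up over 12 weeks with T1 at week 1 (1/12 ≈ 0.08). An f of 0.30 corresponds to a two-week half-life (1 − 0.5^(1/2) ≈ 0.29).

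Two losses should be kept apart. At r = 0.6, going from 71% to 61% is the price of a change score instead of baseline adjustment. Going from 61% to 54% or 35% is the price of starting after treatment has acted, and only that second step also biases the estimate.

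**The case against.** The strongest reply is that little of importance is lost.

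- BSI, the other first-ranked ideation measure, is marked at T0, as are BDI-II, PHQ-9, GAD-7 and SCS-R. The ideation and depression trajectories in the objectives therefore have baselines. **This stands.** The gap concerns half of one rank and three unranked scales, and all secondary results are declared exploratory.
- Randomization keeps post-treatment group comparisons unbiased, and T0 BSI or BDI-II can serve as a covariate for C-SSRS ideation or MADRS. **This stands**, although a different scale will usually correlate less well than the same one, so the precision gain is smaller.
- T1 might fall before session 1, in which case treatment has not acted. **This cannot be excluded**, because no section dates T1. The Weekly Follow-up row argues for a post-baseline week but does not settle it.

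A reader might infer that the primary endpoint is compromised. The protocol does not support that. Time zero is randomization, only later attempts count, and an attempt between screening and randomization is recorded as a baseline event. Dates are checked against clinical or emergency records where available, there are weekly blinded calls, and a separate blinded clinician adjudicates each event. The Cox model uses no baseline C-SSRS score. What remains is the undefined start of the first look-back window.

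A reader might also take the five-visit list in the abstract and conclude that the first C-SSRS value comes at week 6, with a far larger loss. That combines two schedules: the five-visit list includes a baseline, and the table without one starts at T1. Nor do the documents show any error in the clinical-history form that records prior attempts, so there is no ground for changing the source of that stratification factor.

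**Conclusion.** The schedule omits a pre-allocation value for C-SSRS ideation, MADRS, NIH-BFI and FSS, and in doing so contradicts the protocol's text. The consequence is a weaker group×time analysis for those four scales. Under the stated assumptions (56 per arm, d = 0.38, r = 0.6), power falls from about 71% with baseline adjustment to about 61% with a change from T1 and no early effect. It falls to about 54% or 35% if 8% or 30% of the effect is already present at T1, and the estimate then shrinks to 0.35 or 0.27. The correlation and the early shares are not in the documents. For a given early share, the direction of the bias does not depend on the correlation. The bias itself depends on T1 falling after treatment has begun, which is the likelier reading but not a documented one.

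This should be fixed before recruitment, but it does not threaten the primary analysis.

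**What to change.** 1. In Table 2, mark C-SSRS, MADRS, NIH-BFI and FSS at T0.
2. State that T0 is completed before randomization. The Randomization section could say that the enrollment step locked in REDCap includes the T0 battery.
3. Place T1–T15 in calendar time relative to randomization and session 1, and reconcile them with the five assessment points in the abstract.
4. State that the C-SSRS look-back at T1 starts at the randomization date.

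If the sponsor intends T1 to precede randomization, saying so would answer the baseline concern for these scales. In that case the look-back at the first C-SSRS after randomization should start at the randomization date.

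Cost: a table correction, a few sentences, and a longer baseline visit with four added instruments. All four are already given at every later visit, so no new tools are needed. The added time must be checked against the 60-minute ceiling in Measurement Battery: Prioritization and Burden. No extra participants are required.
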